#### **6.4. Secondary objective 1**

*To determine the time to culture-conversion of the Moxifloxacin regimen and the Ethambutol regimen using data from 2-, 4-, 6-, and 8-week cultures*

Time to culture conversion is defined as the time from treatment initiation to the date of the first of two negative cultures at two different visits without an intervening positive culture. Kaplan–Meier curves and the Gehan-Breslow-Wilcoxon test will be used to compare time to culture conversion across the two arms. Proportional hazards regression will also be used to assess whether time to culture-conversion differs across the two arms.

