## 7. CLINICAL AND LABORATORY EVALUATIONS

### 7.1 Schedule of Events (SoE)

**Table 5: Study Table of Evaluations**

Procedures	Screening	Baseline	Week			Study Months														
			2	4	6	2	3	4	5	6	7	8	10	12	14-24 (*2 monthly)	End TB Treat	Recurr ence 	Termi nation	Time of IRIS	Time of Serocon version
Inclusion & Exclusion Criteria		X																		
Informed Consent	X																			
Randomization		X																		
HIV test (performed monthly for HIV negative participants)	X 		X			X	X	X	X	X	X	X	X	X	X	X	X	X	X	X
Medical , Medication and TB History & Physical Exam	X	X	X			X	X	X	X	X	X	X	X	X	X	X	X	X	X	X
Vitals (including Pregnancy test )	X	X	X			X	X	X	X	X	X	X	X	X	X	X	X	X	X	X
Contraception confirmation	X	X	X			X	X	X	X	X	X	X	X	X	X	X	X	X		
Concomitant medications	X	X	X			X	X	X	X	X	X	X	X	X		X				
GeneXpert	X																			
Sputum Smear	X	X	X			X	X	X	X	X	X	X	X	X	X	X	X	X		
Culture : INTERVENTION ARM: until 6 months		X	X	X	X	X	X	X	X	X					X	X	X			
Culture: CONTROL ARM: until 6 months		X	X	X	X	X	X	X	X	X					X	X	X			
Susceptibility		X				X				X*		X*				X	X			
PAXgene for SHIP Study		X				X				X		X			X	X	X	X		
Urine (Lam Testing)		X				X			X	X						X				
Chest radiograph		X 					X			X						X	X			
ECG **		X				X		X		X										
Vision testing (Snellen and Ishihara) Control Arm only		X				X														

Procedures	Screening	Baseline	Week			Study Months											End TB Treatment	Recurrence	Termination	Time of IRIS	Time of Seroconversion
			2	4	6	2	3	4	5	6	7	8	10	12	14-24 (*2 monthly)						
AST, ALT, Bilirubin, Hb, platelets, & Full blood count, Creatinine clearance, potassium, total protein, alkaline phosphatase and as clinically indicated	X	X 				X		X		X							X	X	X	X	X
CD4 Count ( HIV Infected patients only )	X					As per SA HIV guidelines														X	
Viral Load ( HIV Infected patients only )	X																	X		X	
HBsAg	X																				
PK Samples (Intervention Arm)				X		X 3				X	X 										
PK Samples (Control Arm)						X															
Specimen Storage		X	X		X		X						X				X				X
PBMCs***		X 				X				X					X	X	X	X	X	X	X

1: HIV Testing is required at screening for all potential participants. Thereafter, HIV testing will be required for HIV negative participants only as per SoE above.

2: A chest radiograph/Bloods will be repeated if they are more than 14 days old

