3: PK blood samples, in the intervention arm only, will be taken once during the intensive phase of TB treatment at either Week 4 **OR** Month 2 (**PK bloods may be repeated at Month 2 if these were not taken, incorrectly done or incomplete at Week 4 OR at the discretion of the investigator**), and at the end of TB treatment (Month 6)

4: Additional PK samples will be taken at M7 (or the first visit after if Month 7 is missed) in Intervention Arm before and after the ingestion of the single additional dose of Moxifloxacin. This additional PK sample may be deferred to month after TB treatment completion on participants who have TB treatment extended beyond 6 months

5: If PBMCs are not collected at baseline samples may be taken at Week 4 or Month 2

6. End of TB Treatment visit will be conducted within 7 days of completion of TB treatment.

\* Samples will be collected and stored for future susceptibility testing,

\*\*ECG's will be done at baseline, Month 2 and Month 4 and Month 6. ECG's will be performed 2 monthly during treatment with Moxifloxacin

\*\*\*Additional PBMC's will be collected at IRIS and at the time of seroconversion

The study SoE will be followed except when procedures are clinically indicated as not required.

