#### Study visits – continuation phase of therapy

Intervention arm - study visits Month 3 to Month 6 will be considered as continuation phase.

Control arm - study visits Month 3 to Month 6 will be considered as continuation phase.

Month 4 – Patients will have an assessment for toxicity from the four-drug phase of therapy. This will consist of a symptom-driven examination, and laboratory testing (complete blood count and serum AST, total bilirubin, and serum creatinine). A sputum specimen will be obtained for culture.

Month 4-6–Patients will continue to have study visits monthly during the continuation phase of therapy. Sputum cultures will be obtained at Month 4, Month 5, Month 6 during the continuation phase of therapy. Laboratory testing, other than sputum cultures, will be at the discretion of the principal investigator/study clinician.

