## 6.3. Primary objective

*To determine if a Moxifloxacin-containing regimen, [Isoniazid (H), Rifampicin (R), Pyrazinamide (Z), Moxifloxacin (M)] of 24 weeks duration is superior to a control regimen [Isoniazid (H), Rifampicin(R), Pyrazinamide (Z), Ethambutol (E)] of 24 weeks duration in improving treatment outcomes in patients with recurrent TB.*

To answer the primary objective of this study the culture conversion rates will be compared between the two treatment arms at the end of the intensive phase and at month 6, where culture conversion is defined as the first of two negative (or no growth) cultures at two different visits without an intervening positive culture. This will be done by calculating the proportion of culture conversions in each of the two arms and at each of the two time points and comparing these using the chi-square test or Fisher's exact test. Log binomial regression

or Poisson regression with robust variance will also be used to improve precision of the treatment effect estimates.

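### SAP 6.4: on the 2- to 8-week cultures alone, a first negative at week 8 can never count as a conversion event

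*SAP*

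**What the plan says.** For secondary objective 1, SAP 6.4 names the cultures to be used: "using data from 2-, 4-, 6-, and 8-week cultures". It measures time from treatment start to "the first of two negative cultures at two different visits without an intervening positive culture". The analysis is by Kaplan-Meier curves, the Gehan-Breslow-Wilcoxon test and proportional hazards regression.

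SAP 6.3 applies nearly the same rule to the primary objective, "the first of two negative (or no growth) cultures at two different visits without an intervening positive culture", and compares proportions "at the end of the intensive phase and at month 6". It does not list which cultures may be used and sets no window for the confirming culture. SAP 6.6 reuses conversion at the end of the intensive phase for the comparison by HIV status.

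In the protocol's schedule of events (Table 5), cultures are ticked in both arms at baseline, weeks 2, 4 and 6, and months 2, 3, 4, 5 and 6. The 8-week culture is the month 2 visit. The culture rows are labelled "until 6 months". In the text available for review they are also ticked at months 14-24, end of TB treatment and recurrence.

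**The concern.** A rule needing two negatives requires at least one culture after the last date on which an event can occur. SAP 6.4 stops the named data at that last date. Read literally, the curve cannot step at week 8, and a patient who truly converts between weeks 6 and 8 is treated as not converted.

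The SAP does not say whether such a patient is a non-event, is censored, or may be confirmed by a later culture. The missing-data rule in SAP section 5 does not settle it, because the week 8 culture is present. Two analysts could therefore follow the plan and report different curves. In an open-label trial that choice should be fixed in advance.

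**Working it through.** **1. The plan's own figure (for the number per arm).** Protocol 9.1: 75% v 60%, two-sided 0.05, 80% power, continuity-corrected chi-square, 330 in total; SAP section 2: 1:1 allocation.

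- Uncorrected: n' = [1.960·√(2·0.675·0.325) + 0.842·√(0.75·0.25 + 0.60·0.40)]² / 0.15² = 151.9, that is 152 per arm.
- Corrected: n = (n'/4)·[1 + √(1 + 4/(n'·0.15))]² = 164.9, that is 165 per arm.
- Total 330, which matches.

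**2. Which event dates are attainable.** All positive/negative patterns were listed for each set of cultures, and the two-negative rule was applied.

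| Cultures available | Dates an event can take |
|---|---|
| Weeks 2, 4, 6, 8 | weeks 2, 4, 6 |
| The same plus month 3 | weeks 2, 4, 6, 8 |
| All through month 6 | every visit to month 5, not month 6 |
| The same plus one later culture at a separate visit | every visit including month 6 |

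For example, positive at weeks 2, 4 and 6 and negative at week 8 gives no event on the first row. With a negative month 3 culture it gives an event at week 8.

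**3. Illustrative size.** Assumptions, none of which the documents give:
- The design rates of 60% and 75% are reached by week 8 (protocol 9.1 attaches no date to them).
- The conversion rate is constant.
- No cultures are missed, and every first negative would be confirmed.

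For a proportion p converted by week 8, the proportion countable by week 6 is 1 − (1 − p)^(6/8). The share first negative at week 8 is (1 − p)^0.75 − (1 − p).

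- Control: 0.503 − 0.400 = 0.103. Countable 49.7%; 165 × 0.103 = 17 patients; 0.103/0.60 = 17% of that arm's events.
- Intervention: 0.354 − 0.250 = 0.104. Countable 64.6%; 165 × 0.104 = 17 patients; 0.104/0.75 = 14% of that arm's events.
- Both arms: events expected 165 × 0.60 + 165 × 0.75 = 99 + 123.75 = 222.75; lost about 34; 34/222.75 = 15%.

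**4. Range.** If instead 10%, 20% or 30% of each arm's events are first negatives at week 8, the events lost are:
- Control: 99 × share = 10, 20 or 30.
- Intervention: 123.75 × share = 12, 25 or 37.

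**5. Effect on the hazard ratio.** With no events possible at week 8 in either arm, that visit adds nothing to the estimate. Using √(1/e₁ + 1/e₂) as a rough standard error of the log hazard ratio:
- All events: √(1/99 + 1/123.75) = 0.135.
- Under step 3, with 82 and 107 events left: √(1/82 + 1/107) = 0.147, about 9% larger.

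Under proportional hazards this costs precision but need not bias the ratio. The curve at week 8 would be read too low.

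**The case against.** The strongest reply is that the listed weeks belong to the wording of the objective, while the sentence defining the event places no limit on the confirming culture. SAP section 5 says all non-missing time points are used, and month 3 is scheduled. An analyst could therefore confirm a week 8 negative at month 3 without breaking the plan. That is a fair reading and the sensible one, but the SAP does not state it, and the list of cultures in 6.4 points the other way.

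Two stronger inferences are tempting, and the documents do not support either.

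- **That the primary proportions are understated.** A reader might carry 49.7% v 64.6% into SAP 6.3 and conclude that continuity-corrected power falls from 80% to about 75%. The 2- to 8-week limit appears only in secondary objective 1. SAP 6.3 dates conversion at the first negative and leaves the confirming culture open, so on a plain reading a negative at the end of the intensive phase confirmed at month 3 already counts.
- **That a first negative at month 6 can never be confirmed.** The "until 6 months" label, and protocol 7.2.3 ("Sputum cultures will be obtained at Month 4, Month 5, Month 6 during the continuation phase of therapy"), suggest this. But the culture rows are also ticked at end of TB treatment and at months 14-24, and protocol 7.3.2 refers to positive cultures through month 8. A patient whose treatment is extended for late conversion would have a later, separate end-of-treatment visit. For a patient finishing on time that visit may coincide with month 6, since "End of TB Treatment visit will be conducted within 7 days of completion of TB treatment", so some gap remains. Its harm is not shown. With all cultures taken, a first negative at month 6 means a positive month 5, which already meets the protocol's definition of treatment failure (patients found to have rifampicin- or multidrug-resistant TB aside).

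**Conclusion.** The point holds for secondary objective 1. As written, SAP 6.4 names four cultures but allows events at only three of them, and it has no rule for an unconfirmed negative at the last one. The loss is about 17 patients per arm, roughly 15% of events, under a constant rate reaching the design proportions at week 8. The true share is not in the documents, and the loss scales directly with it.

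For the primary analysis and SAP 6.6 the finding is only that the confirming culture is unstated. For month 6 it is that the protocol's statements about later cultures disagree and need reconciling. The positions of the ticks after month 6 come from a table extracted from PDF and should be checked against the original.

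**What to change.** **SAP 6.4.** State that:
- a first negative at week 8 is an event dated at week 8 if the next available scheduled culture is negative (month 3, or the next one if month 3 is missing);
- an unconfirmed week 8 negative is censored, with the censoring date given, because censoring at week 8 itself leaves the patient at risk and unconverted at that visit, whereas an earlier date does not;
- a sensitivity analysis counts unconfirmed week 8 negatives as events.

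**SAP 6.3 and 6.6.** State that any later scheduled culture may confirm a negative at the end of the intensive phase, including an extended one. Leave the definition of conversion otherwise unchanged.

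**Month 6.** Reconcile the label on the culture rows, the later ticks and the month 8 storage text. State that a later culture at a separate visit may confirm a first negative at month 6. Do not require the month 6 culture itself to be negative: a patient with two earlier negatives has already converted under SAP 6.3, and a missed month 6 culture should not reverse that.

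**Cost.** A few sentences and one sensitivity analysis. It adds no visits or samples. The trade-off is that confirmation draws on one culture beyond the 8-week window.

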#### **6.5. Secondary objective 2**

*To compare the proportion of patients with any Grade 3 or 4 adverse reactions*

Adverse events occurring during the study will be summarised in frequency tables by arm. The frequencies of Grade 3 and 4 adverse events will be compared between the two arms using the Fisher's exact test.

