## SCHEMA

**Design:** This is an open label randomized controlled clinical trial comparing two regimens for treatment of smear-positive pulmonary TB, among patients previously treated for TB. The primary objective is to determine if a Moxifloxacin-containing regimen, substituting Moxifloxacin for Ethambutol, of 24 weeks duration is superior to a control regimen of 24 weeks duration in improving treatment outcomes in patients with recurrent TB.

**Duration :** Intervention Arm : Approximately 6 months treatment + 12 months post treatment follow up

Control Arm : Approximately 6 months treatment + 12 months post treatment follow up

**Sample Size:** 330

**Population :** This study will include adults 18 years and over with a previous history of TB. HIV infected and uninfected patients will be included in the study as well as patients on ARVs provided that these are not contra-indicated with any of the study drugs. Patients with *M tuberculosis* resistance to Rifampicin will be excluded at screening using Gene Xpert technology.

**Randomization:** Patients will be randomized to receive 1 of 2 TB retreatment regimens

[figure not shown]

Figure 1 : IMPRESS patient screening and randomization arms

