### **2.2 Secondary Objectives**

- 2.2.1 To determine the time to culture-conversion of the Moxifloxacin regimen and the Ethambutol regimen using data from 2-, 4-, 6-, and 8-week cultures
- 2.2.2 To compare the proportion of patients with any Grade 3 or 4 adverse reactions
- 2.2.3 To compare adverse events and 2-month culture conversion rates among HIV-infected patients vs. HIV-uninfected patients
- 2.2.4 To compare the rates of treatment failure and recurrence of the Intervention and Control arm.
- 2.2.5 To compare TB cure rates at month 6 and at end of TB treatment between the Intervention and Control Arm

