### 8.2.5 Reporting AE's

The study drugs are Moxifloxacin, Ethambutol, Isoniazid, Rifampicin, and Pyrazinamide. The most common adverse effects known to be associated with the study drugs are summarized in the protocol (see Table 4 above). The investigators are responsible for reporting all Grade 3 and Grade 4 adverse events that are observed or reported during the study, regardless of whether they are thought to be related to the study drugs in patients chart notes. All Adverse Events including SAEs will be reported in accordance with ICH and SA GCP guidelines.

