## 8.5 Safety Monitoring

### Procedures for assessing safety

At each clinic visit patients will be asked about changes (adverse events) that have occurred since their previous visit. Physical assessments will be performed at baseline and on subsequent scheduled visits.

Safety laboratory investigations will be performed at screening and in accordance with the schedule of evaluations, as well as determined by the study clinician based on the evaluation.

1. Screening tests and scheduled subsequent visits will include: Liver function, renal function, full blood count: At screening, baseline and every second month until Month 8 of follow up. Thereafter, tests will be performed at the end of TB treatment, time of TB recurrence and at the study termination visit.
2. 2. Pregnancy test: At screening, baseline and every month thereafter as per the SoE.

For isolated asymptomatic or symptomatic Grade 3 elevation of total bilirubin all medications should be discontinued and held for up to 14 days until levels and symptoms are Grade  $\leq 2$ , at which time therapy may be reintroduced. If there is  $\geq$  Grade 2 elevation of total bilirubin with transaminase elevation of grade  $\geq 3$ , this

should be treated as Grade 4. If Grade 3 toxicity develops after re-introduction of the study medications or if the Grade 3 toxicity does not resolve within 14 days, then the participant will be discontinued from study medications. The participant will continue to be followed on study, off study drugs. All medications may be restarted if the laboratory abnormalities were thought secondary to a concomitant illness.

Participants who develop Grade 4 elevations of the total bilirubin will be discontinued from study medications. The participant will continue to be followed on study, off study drugs.

Any additional test that the investigator deems necessary for the clinical evaluation of the subject can be performed.

Any adverse events detected will be graded according to a modified version of the toxicity criteria produced by the Division of AIDS and coded using MedDRA.

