## 2. STUDY DESIGN

This is an open label randomized controlled clinical trial comparing two regimens for treatment of smear-positive pulmonary TB, among patients previously treated for TB. The primary objective is to determine if a Moxifloxacin-containing regimen, substituting Moxifloxacin for Ethambutol, of 24 weeks duration is superior to a control regimen of 24 weeks duration in improving treatment outcomes in patients with recurrent TB.

This study will include adults 18 years and over with a previous history of TB. HIV infected and uninfected patients will be included in the study as well as patients on ARVs provided that these are not contra-indicated with any of the study drugs. Patients with M tuberculosis

resistance to Rifampicin will be excluded at screening using Gene Xpert technology. A maximum of 330 participants will be included in the study.

Patients will be randomized in a 1:1 ratio to receive one of the two TB retreatment regimens, as outlined in the table below.

|                         | Intensive Phase (2 months) | Continuation Phase |
|-------------------------|-----------------------------------|---------------------------|
| Intervention Arm | HRZM* daily (2 months)            | HRM* daily (4 months)     |
| Control Arm      | HRZE* daily (2 months)            | HR* daily (4 months)      |

\* Isoniazid (H), Rifampicin (R), Pyrazinamide (Z), Moxifloxacin (M), Ethambutol (E)

The duration of TB treatment may increase due to a delay in the time to sputum conversion which will result in the extension of TB treatment beyond 6 months. Following treatment, participants will be followed up on a two-monthly basis for 12 months.

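### The Grade 3/4 safety comparison is aimed at adverse reactions but is written as events of any cause with no on-treatment window, so post-treatment events can dilute a difference between the regimens

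*SAP*

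**What the plan says.** Protocol 2.2.2 sets the objective: "To compare the proportion of patients with any Grade 3 or 4 adverse reactions". The SAP repeats it in 1.2 and again above the method in 6.5.

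The method in SAP 6.5 has two sentences. The first is about tabulation: "Adverse events occurring during the study will be summarised in frequency tables by arm". The second is the test: "The frequencies of Grade 3 and 4 adverse events will be compared between the two arms using the Fisher's exact test".

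On collection, the rule in Protocol 8.2.5 covers "all Grade 3 and Grade 4 adverse events that are observed or reported during the study, regardless of whether they are thought to be related", so causality plays no part in it. Protocol 8.5 adds: "At each clinic visit patients will be asked about changes (adverse events) that have occurred since their previous visit".

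On duration, the protocol schema gives, for each arm, "Approximately 6 months treatment + 12 months post treatment follow up". SAP section 2 agrees: "Following treatment, participants will be followed up on a two-monthly basis for 12 months".

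No other section supplies a window. SAP section 3 describes who is in the safety summaries but sets no time limit. The per-protocol set in SAP section 4 drops data after treatment interruptions of three months or more, which does not define time on treatment.

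**The concern.** A reaction is an event attributed to a drug. An analysis can approach that in two ways: by a causality judgement, or by restricting to the period when the drug could be acting. SAP 6.5 does neither. Read as written, a Grade 3 event a year after the last dose counts the same as one in week 3.

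Events unrelated to either regimen add background to both arms. This hides a real difference in either direction, whether from moxifloxacin (planned for all 6 months of its arm) or from ethambutol (planned for 2 months of its arm). In a safety comparison, the error at stake is finding no clear difference because the window was too wide.

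**Working it through.** **The plan's own figure.** No power or rate is stated for the Grade 3/4 comparison. The only stated size is 330 in Protocol 9.1, for 75% v 60%, 80% power, two-sided 0.05, continuity-corrected chi-square.
- Uncorrected: n = [1.96·√(2 × 0.675 × 0.325) + 0.8416·√(0.75 × 0.25 + 0.60 × 0.40)]² / 0.15² = 151.9, i.e. 152 per arm.
- Corrected: (151.9/4)·[1 + √(1 + 4/(151.9 × 0.15))]² = 164.9, i.e. 165 per arm, or 330 in total.

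The figure reproduces, and 165 per arm (1:1 allocation, SAP section 2) is used below.

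**Share of planned time after treatment.**
- 12/(6 + 12) = 67%.
- If treatment is extended by 1, 2 or 3 months (extension is allowed, its length is not given): 12/19 = 63%, 12/20 = 60%, 12/21 = 57%.
- If visits run to month 24, as the Schedule of Events columns do: 18/24 = 75%.

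**Dilution.** Let p be the on-treatment risk of at least one Grade 3/4 event and b an independent post-treatment risk, equal in both arms.
- Whole-study risk = 1 − (1 − p)(1 − b).
- Risk difference = (p₁ − p₀)(1 − b), so it shrinks by (1 − b) whatever the rates.

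**Illustration.** All rates are assumptions. Power is exact for the two-sided Fisher test that SAP 6.5 names, at 165 per arm and 0.05.

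| b | Whole-study risks | Difference | Risk ratio | Fisher power |
|---|---|---|---|---|
| 0 (on-treatment only) | 10.0% v 20.0% | 10.0 points | 2.00 | 0.68 |
| 5% | 14.5% v 24.0% | 9.5 | 1.66 | 0.54 |
| 10% | 19.0% v 28.0% | 9.0 | 1.47 | 0.44 |
| 20% | 28.0% v 36.0% | 8.0 | 1.29 | 0.31 |
| 30% | 37.0% v 44.0% | 7.0 | 1.19 | 0.22 |

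A larger assumed effect is hurt less at low background. With 10% v 25% on treatment, power is 0.94 in the window and 0.86, 0.77, 0.60 and 0.45 at the same four values of b.

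**A rough guide to b.** Suppose the 10% control risk over 6 months were all background and continued at the same hazard for 12 months. Then b = 1 − 0.90² = 19%, giving 27.1% v 35.2%, risk ratio 1.30, power 0.32. At half that hazard, b = 1 − 0.90 = 10%, the third row of the table.

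**The case against.** **Two thirds is a share of time, not of events.** ECGs are scheduled at baseline and months 2, 4 and 6. Protocol 8.5 schedules safety bloods every second month to month 8, then only at end of treatment, recurrence and termination. Post-treatment visits are two-monthly. Abnormalities found by scheduled tests will therefore be picked up mostly on treatment. This stands: b may be small, and a reader should not infer that two thirds of the counted events will be off drug.

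**The test sentence names no window.** The words about the whole study sit in the tabulation sentence, and Protocol 8.2.5 is a rule for reporting in chart notes. A reader might infer that the SAP explicitly chose a whole-study, all-cause test. It did not; that is only the natural reading. But if the tested period is not whole-study, it is undefined, and that also needs correcting.

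**A whole-study count by randomised arm is a legitimate comparison and captures late harm.** True, and it should be kept as supportive. It is not a good main measure for an objective about reactions.

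**A last-dose window has its own flaw.** Treatment length depends on sputum conversion and missed doses, so the window is longer in slow converters and shorter in patients stopped early. Conversion is the primary outcome, so windows could differ by arm. This stands and is met by a fixed-window sensitivity analysis. A window covering the whole regimen also includes months after planned ethambutol ends, which is acceptable because regimens are being compared.

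**Equal background is an assumption.** If recurrence differs by arm, late events may differ too, and the distortion need not be simple dilution.

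**It is tempting to extend the point to SAP 6.6.** The documents do not support that. Objective 3 already says adverse events, and the comparison there is by HIV status within arm, so the dilution argument does not carry over.

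**Conclusion.** The mismatch is real: reactions in the objective, all-cause events in the method, and no window in either document. The direction of the effect follows from the algebra if post-treatment risk is similar in the two arms. Its size cannot be derived from the documents. The fall from 0.68 to between 0.54 and 0.22 holds only for the assumed 10% v 20% and b of 5% to 30%.

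A reader might go further and conclude that the trial will miss a harm of moxifloxacin. That is not supported: there are no Grade 3/4 rates, and the monitoring schedule may keep the loss small. The point concerns one secondary objective with no stated power and leaves the primary analysis untouched. It should be corrected because the remedy is cheap and the present wording leaves a finding of no difference hard to interpret.

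**What to change.** Amend SAP 6.5 only:

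1. Define the tested outcome as the proportion of patients with at least one Grade 3 or 4 event of any cause, with onset from first dose to a pre-stated interval (for example 30 days) after the last dose of study TB treatment. Counting patients rather than events also gives Fisher's test the one binary outcome per patient that it needs. All-cause counting is preferable to a relatedness filter for the main test, because relatedness is judged open-label.
2. State how the single month-7 moxifloxacin dose in the PK sub-study is handled. It is taken by intervention-arm patients only and falls near the edge of a 30-day window.
3. Add a sensitivity analysis with a fixed window from treatment start, the same in both arms (for example 7 months).
4. Report post-treatment, whole-study and investigator-related Grade 3/4 events by arm as supportive.

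The cost is SAP wording and a few tables. Late events leave the tested comparison but remain visible. The documents do not say that event onset and last-dose dates are recorded, although an end-of-treatment visit and pill counts on a CRF are described. Their availability on the CRF must be confirmed before the window is fixed.

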## 5. GENERAL STATISTICAL ISSUES

All tests will be two-sided, and the significance level will be 0.05.

Outliers will be identified by looking at summary statistics and scatter plots. All outliers detected will be verified from the source documentation. Outliers that have biologically impossible values will be excluded from all data summaries and analyses. If one (or several) outlier(s) change(s) the interpretation of the data substantially, two summaries and analyses will be done, one with and one without the outlier(s).

If a participant has missing data at a specific time point, data at all non-missing time points for the participant will be used and included in the summaries. Missing data will be ignored (i.e. treated as missing at random) unless patterns are identified which would potentially bias analysis results.

Where applicable, analyses will be stratified by HIV status.

All statistical analyses will be done using SAS (SAS Institute Inc., Cary) version 9.4 or higher.

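### SAP 6.5 sets a per-patient objective for Grade 3 or 4 harm but plans only a Fisher's exact p-value on event frequencies, with no risk difference or interval to show how large an excess the trial can exclude

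*SAP*

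**What the plan says.** SAP 6.5 restates the objective as "To compare the proportion of patients with any Grade 3 or 4 adverse reactions". The method has two parts. The first is descriptive: "Adverse events occurring during the study will be summarised in frequency tables by arm". The second is the only between-arm inference: "The frequencies of Grade 3 and 4 adverse events will be compared between the two arms", by Fisher's exact test. SAP section 5 sets the threshold: "All tests will be two-sided, and the significance level will be 0.05".

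No risk difference, risk ratio, interval or upper bound for harm appears in SAP 6.5, SAP section 5 or protocol section 9. Effect estimates are planned elsewhere. SAP 6.3 adds log-binomial or robust Poisson regression, which "will also be used to improve precision of the treatment effect estimates", and SAP 6.4 adds proportional hazards regression for time to conversion. SAP 6.7 (failure and recurrence) and SAP 6.8 (cure) name only tests, as 6.5 does.

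The size of the comparison follows from SAP section 2: "A maximum of 330 participants will be included in the study" and "Patients will be randomized in a 1:1 ratio".

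**The concern.** There are two problems in the same sentence of SAP 6.5.

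First, the unit. The objective counts patients and refers to reactions; the method counts frequencies of events. Fisher's test assumes independent observations, so it is not valid if one patient contributes several events. Reactions and events are also not the same thing unless the SAP says so.

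Second, the output. The sample size in protocol 9.1 rests on a 15-point difference in culture conversion. A trial of that size will often return a non-significant result for harms that matter. A p-value alone cannot then separate no excess from an excess that was not detected. Protocol 9.3 and 10.2 present the trial as evidence for retreatment policy, so readers will want to know how much additional Grade 3 or 4 harm the data rule out. The plan does not commit to telling them.

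**Working it through.** **Inputs from the documents.** N = 330 and 1:1 allocation (SAP section 2), so n = 165 per arm; two-sided alpha 0.05 (SAP section 5); 75% against 60% conversion, 80% power, continuity-corrected chi-square (protocol 9.1).

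**Assumed, because the documents give no figure.** The control Grade 3 or 4 rate (1% to 40%, with 5% to 10% as the working case); an excess of interest of 5 points; no loss of patients (varied below).

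**Step 1: the plan's own sample size.** With p̄ = 0.675 and d = 0.15,

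n₀ = [1.96·√(2·0.675·0.325) + 0.842·√(0.75·0.25 + 0.60·0.40)]² / 0.15² = 151.9.

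Continuity correction: n = (n₀/4)·[1 + √(1 + 4/(n₀·d))]² = 164.9, which rounds up to 165 per arm, or 330. The stated figure is reproduced.

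**Step 2: power of the planned safety test.** Power = Σ Bin(x; 165, p_T)·Bin(y; 165, p_C) over all tables (x, y) with Fisher p ≤ 0.05, where Fisher p sums the hypergeometric probabilities no larger than that of the observed table.

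| Control rate | Intervention rate | Power | Missed |
|---|---|---|---|
| 1% | 6% | 62.0% | 38% |
| 3% | 8% | 42.3% | 58% |
| 5% | 10% | 32.7% | 67% |
| 10% | 15% | 22.7% | 77% |
| 20% | 25% | 16.0% | 84% |
| 40% | 45% | 12.8% | 87% |

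For control rates of 5% to 10%, the miss rate is 70% to 79% with 150 per arm and 75% to 82% with 132 per arm. At 165 per arm, the excess detectable with 80% power is about 10 points at a 5% control rate, 12 points at 10% and 14.5 points at 20%.

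**Step 3: what an interval would show.** Take 26/165 intervention (15.8%) against 16/165 control (9.7%).

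- Fisher p = 0.136.
- Risk difference = 10/165 = 6.1 points.
- Standard error = √(0.1576·0.8424/165 + 0.0970·0.9030/165) = 3.65 points.
- Wald 95% interval: 6.1 ± 1.96·3.65 = -1.1 to +13.2 points.
- Miettinen-Nurminen 95% interval (unstratified): -1.2 to +13.5 points.

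The plan would report p = 0.14. The interval shows that an excess of 13 points is still compatible with the data.

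**Step 4: precision of the proposed estimate.** Half-width = 1.96·√([p_T(1-p_T) + p_C(1-p_C)]/165): ±5.7 points at 5% v 10%, ±7.1 at 10% v 15%, and ±9.0 at 20% v 25%.

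**Step 5: Fisher against chi-square.** The same enumeration for the continuity-corrected chi-square, the only variant the documents name (protocol 9.1), gives 32.7% and 22.7% in the 5% v 10% and 10% v 15% cases, the same as Fisher. The uncorrected test would give 40.7% and 28.1%.

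**The case against.** The other side has good arguments. Low power for harms is normal in a trial sized for efficacy, and adding an interval does not change the miss rate. Fisher's test is a standard choice for counts that may be sparse. Frequency tables by arm are planned, so if they count participants anyone can compute the crude difference and its interval. The safety committee also reviews adverse events by arm, using judgement and no p-value rule (SAP section 3). And the SAP could be followed as written with an interval added at the reporting stage.

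Most of this stands, and it limits the point. It does not remove it. SAP 6.5 does not say that the tables count participants, the interval is not pre-specified, and committee monitoring is not the final between-arm analysis.

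Four stronger readings are tempting, and the documents do not support them:

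- *A non-significant result will be taken as evidence of safety.* No passage says so. What can be said is that such a result could not exclude a material excess.
- *Estimates are planned only for the primary endpoint.* SAP 6.4 plans proportional hazards regression, which yields a hazard ratio, and SAP 6.7 and 6.8 share the gap in 6.5. The omission is not confined to harm.
- *Fisher's test makes matters worse than the chi-square.* Step 5 shows no penalty against the only chi-square variant the documents name. A gap appears only against an uncorrected version that they never specify.
- *The 67% to 77% miss rate is a property of the plan.* It depends on an assumed control rate and an assumed excess.

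**Conclusion.** The point holds as a low-cost improvement to the analysis plan. It is not an error that invalidates a result. SAP 6.5 moves from patients and reactions in its objective to frequencies of events in its method, and a p-value is its only inferential output.

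The case for an interval rests on its width more than on the power table. With 165 per arm the 95% interval for the excess will span roughly ±6 to ±9 points at control rates of 5% to 20%, and a reader who sees only p above 0.05 has no way to know that. The miss rates (67% to 77% at control rates of 5% to 10%; 38% to 87% at 1% to 40%) illustrate the same limit and assume a 5-point excess and full follow-up. With fewer evaluable patients they rise.

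**What to change.** Replace the comparison sentence in SAP 6.5 with wording such as:

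> *The number and percentage of participants with at least one Grade 3 or 4 event will be given by arm. Arms will be compared by the risk difference (intervention minus control) with a two-sided 95% score (Miettinen-Nurminen) interval stratified by HIV status. Fisher's exact p-value, computed on participants, is supportive. The upper limit will be reported as the largest excess compatible with the data.*

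In the same section, state whether the analysis counts all events or only those judged to be reactions, so that objective and method agree. Report the same estimate and interval for failure and recurrence in SAP 6.7 and for cure in SAP 6.8.

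Stratifying by HIV status matches the randomisation (protocol section 5) and the general rule in SAP section 5.

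The cost is SAP text and a few lines of SAS; no new data, visits or patients are needed. The one downside is that an interval of about ±6 to ±9 points makes the safety statement look less favourable than a bare non-significant p-value.
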